2.3. Randomization

Subjects will be randomized in a 1:1 ratio to one of two groups (FX-322 or placebo, respectively). The randomization will be stratified for Visit 2 (Day -15) Maryland CNC Word Recognition Score (above or equal to 28% words in quiet correct and below 28% words in quiet correct) and unilateral versus bilateral hearing loss. A single injection of FX-322 or placebo will be administered on Day 1 by intratympanic injection in the study ear.

2.4. Study Population

Male and female adults (18-65 years inclusive), otherwise healthy with acquired sensorineural hearing loss, associated with noise-induced SNHL (NIHL) or idiopathic sudden SNHL (SSNHL).

2.5. Sample Size Determination

The sample size of 112 evaluable subjects, in a 1:1 allocation ratio of FX-322 and Placebo, was selected to provide an overall statistical power of at least 80% to detect a difference in the primary endpoint for word recognition, as defined by the proportion of subjects that exceed the 95% upper confidence limit as described by Carney and Schlauch (2007) in the study ear. The target enrollment of 124 subjects is an adjustment for an assumed 10% study dropout rate. Detailed sample size determination is provided in the unmasked protocol addendum. Each subject contributes one study ear and one non-study ear.

3. GENERAL ANALYSIS AND REPORTING CONVENTIONS

The following is a list of general analysis and reporting conventions to be applied for this study.

- Categorical variables will be summarized using counts (n) and percentages (%) and will be presented in the form n (%). If a count is 0, no percentage will be shown. To ensure completeness, summaries for categorical and discrete variables will include all categories, even if no subjects had a response in a particular category. Missing data for categorical variables will have a 'Missing' category added at the end and the count will be presented without a percentage. Percentages for categorical variables will exclude the 'Missing' category.
- Continuous variables will be summarized using number of evaluable subjects, mean, standard deviation (SD), minimum, maximum, and median. The mean, median, and

confidence intervals (CI) will be rounded and reported to 1 more level of precision than the original observations, and the SD will be rounded and reported to 2 more levels of precision than the original observations. The minimum and maximum will be the same precision as the original data.

- Following SAS default rules, the median will be reported as the rounded average of the two middle numbers if the dataset contains even numbers.
- P-values will be rounded and reported to 3 decimal places if greater than 0.001. If the rounded p-value is less than 0.001, '<0.001' will be reported. If the rounded p-value is >0.999, '>0.999' will be reported. P-values and significant levels will be reported as 0.05 rather than .05.
- No preliminary rounding will be performed; rounding will only occur after analysis. To round, consider digit to right of last significant digit: if < 5 then round down, if ≥5 then round up.
- All listings will be sorted in order of subject and time of assessment (e.g., visit, time, and/or event).
- Dates in listings will be displayed as yyyy-mm-dd (e.g., 2022-01-22).
- Age (in years) will be calculated using the date of birth and the Screening date in the following SAS algorithm: floor((intck('month', date of birth, Screening date) (day(Screening date) < day(date of birth))))/12. In the analysis datasets, tables, and listings, age will be reported as the integer part of the derived age, with no rounding.
- For all efficacy endpoints, including word recognition in quiet (Maryland Consonant-Nucleus-Consonant [CNC] and W-22) and words in noise (WIN), baseline values for analysis will be defined by ear as the average across the pre-treatment timepoints (Lead-in and Day 1) for left and right ears separately. For the analyses of improvement from baseline above upper confidence limits, either per Carney-Schlauch (2007) or Thornton-Raffin (1978), the rounded up average will be used for conservative approach. Left and right ears will be mapped to treated and untreated for analysis.
- For all safety endpoints and other analyses, baseline will be the last non-missing value before study drug administration.
- For efficacy analyses, Day 90 values will be based on the scheduled Day 90 nominal case report form (CRF) recorded visit. If no scheduled visit data is available for the nominal day 90 CRF recorded visits, the non-missing data in either ear from an early termination or unscheduled assessment performed closest to the target day will be used.

- All endpoints which reference a change in percentage of recognized words are calculated as and should be interpreted as a linear change (i.e., observed baseline) and not a relative change (i.e. (observed baseline)/baseline x 100).
- For all shift from baseline analyses, percentages will be based on the number of subjects in each category at baseline and the post-baseline visit.
- All analysis will be performed using the SAS System version 9.4 or higher.

4. ANALYSIS SETS

Analysis sets in this study are defined in the following:

• Full Analysis Set

The Full Analysis Set (FAS) includes all randomized subjects who receive one dose of study drug (regardless of whether a full dose was administered) in the study ear. Subjects will be analyzed according to their randomized treatment group.

• Per Protocol Analysis Set

The Per Protocol Analysis Set (PPAS) includes subjects in the FAS receiving one full dose of study drug in the study ear to be treated per the randomization treatment schedule and without major protocol deviations as defined in Section 6.1. PPAS subjects will be analyzed according to their randomized treatment group.

• Safety Analysis Set

The Safety Analysis Set (SfAS) includes all subjects who receive one dose of study drug (regardless of whether a full dose was administered) in any ear and will be analyzed according to the actual treatment received. For safety assessments completed by ear for each subject, results from actual treated and actual untreated ears will be summarized separately. The SfAS will be used for the analysis of safety.

All main efficacy analyses will be based on FAS, with sensitivity analyses for primary and key secondary endpoint analyses in the PPAS. If more than 10% of subjects in the FAS are excluded from the PPAS, additional sensitivity analyses, other than for the primary and key secondary endpoints based on PPAS, may be performed.

5. STUDY SUBJECTS

5.1. Disposition of Subjects

The disposition of all consented subjects will be tabulated by treatment group and overall. Subjects who failed screening or were not randomized will only be included in the overall column. The following disposition information will be summarized:

Version Date: 2023-01-19

Page 14 of 64

- The number of subjects consented (signed Informed Consent)
- The number and percentage of subjects who failed screening and the reasons for failure
- The number of subjects not randomized and the number of subjects randomized
- The number of subjects in the FAS
- The number and percentage of subjects in the PPAS and SfAS analysis sets
- The number and percentage of subjects who completed the study through Day 90 (Visit 6)
- The number and percentage of subjects who discontinued the study early and the reasons for withdrawal
- The number and percentage of subjects who discontinued the study early for reasons related to COVID-19
- The number and percentage of subjects who continued to the Observational period
- The number and percentage of subjects who completed Day 180 (Visit 7) and Day 270 (Visit 8)
- The number and percentage of subjects who did not complete Day 180 (Visit 7) and Day 270 (Visit 8) and the reasons not completed
- The number and percentage of subjects who did not complete Day 180 (Visit 7) and Day 270 (Visit 8) for reasons related to COVID-19

Percentages for the number of subjects who failed screening and the reasons for failure will be based on the number of consented subjects. All other percentages will be based on number of subjects in the SfAS.

Duration of study follow up (from randomization date to study completion date or early discontinuation visit date) will be summarized in a Kaplan-Meier curve for all randomized subjects by treatment group. Subjects who completed the study will be censored at the study completion date.

Subject disposition data for all randomized subjects will also be listed. A separate bysubject listing for screen failures will be generated along with reason for screen failure.

A listing of all subjects affected by the COVID-19 pandemic (discontinued the study early, had remote visits performed, or missed visits for reasons related due to COVID-19) will be provided to list the impacts of the pandemic on the subject's participation.

5.2. Demographic and Other Baseline Characteristics

Descriptive statistics for demographic and other baseline characteristics will be summarized by treatment group and overall based on FAS. Characteristics to be summarized include:

- Demographic: age, race, ethnicity, sex, height, weight, and body mass index (BMI)
- Hearing loss history: laterality, etiology of hearing loss for treated and untreated ears, duration of hearing loss for treated ears
- History of noise exposure
- Hearing aid use
- Pure Tone Average (0.5, 1, 2, and 4 kHz) for the treated ear
- Bone Conduction Average (0.5, 1, 2, and 4 kHz) for the treated ear
- Word Recognition in Quiet (Maryland CNC) score for the treated ear
- Word Recognition in Quiet (W-22) score for the treated ear
- WIN score for the treated ear
- Patient Global Impression of Severity (PGI-S) Hearing Loss response
- Patient Global Impression of Severity (PGI-S) Daily Impacts response
- Randomization stratum

Demographic and baseline characteristics data will be listed for subjects in the FAS.

6. STUDY OPERATIONS

6.1. Study Conduct

Enrollment will be summarized by site for all enrolled, randomized, and treated subjects, separately. A by-subject listing of batch numbers for all treated subjects will be provided.

The number and percentage of study visits attended will be summarized for subjects in the FAS.

6.2. Protocol Deviations

Protocol deviations will be identified, documented, reviewed, and assessed according to the study protocol deviation guidance. Important or major protocol deviations are those that

might significantly affect the completeness, accuracy, and/or reliability of key study data or that might significantly affect a subject's rights, safety, or well-being.

Major protocol deviations will be listed and tabulated by deviation category for subjects in the FAS by treatment group and overall.

7. ENDPOINT EVALUATION

7.1. Overview of Analysis Methods

7.1.1. Pooling Algorithm

This is a multi-center (US only) study. Unless stated otherwise, data from all participating centers in the study will be pooled for analyses. A site poolability assessment of the primary efficacy analysis will be conducted to assess heterogeneity of the treatment effect between sites. This will be conducted as a descriptive analysis for the primary efficacy endpoint.

7.1.2. Assessment Time Windows

For by-visit summaries, the nominal visit will be used for analysis. Unscheduled visits will be listed but will not be displayed separately in the summaries.

Analysis windows listed in Table 7-1 will be used in the efficacy analyses for slotting actual efficacy assessment date into planned assessment schedule. Early termination visit and unscheduled visit efficacy data will be included in the analyses if no scheduled visit data is available for the nominal CRF visit. If more than one unscheduled assessment (early termination or unscheduled) is performed within an analysis window, the assessment performed closest to the target day will be used.

Visit	Visit Number	Assessment /Day	Target Day	Target Window	Analysis Window ^a
Screening/ Start of Lead-In	1	-40 to -30	N/A	N/A	N/A - Nominal CRF visit
Lead-In Visit	2	-26 to -12	Visit 1 + 16 days	Target day (+/- 2 days)	N/A - Nominal CRF visit
End of Lead-In/ Treatment	3	1	Visit 1 + 35 days	1/Target day (+/- 5 days)	1
In-Clinic Follow-up	4	30	30	25-35 (+/- 5 days)	2-45
In-Clinic Follow-up	5	60	60	55-65 (+/- 5 days)	46-75

In-Clinic Follow-up	6	90	90	85-95	76-135
/Early Termination				(+/- 5 days)	
(ET)					
In-Clinic	7	180	180	173-187	136-225
Observation				(+/- 7 days)	
In-Clinic	8	270	270	263-277	≥226
Observation				(+/- 7 days)	
^a Analysis windows for the Screening and Lead-In Visit are not defined and visit assignments					
are based on the nominal CRF visits. Analysis windows for visits on or after randomization					
are defined using the mid-points between each scheduled visit and will be used to map early					

[figure not shown]
7.1.3. Timing of Analyses

[figure not shown]
termination or unscheduled visit data to scheduled visits.

Primary efficacy analysis will be conducted after all subjects have either completed the follow-up visits (Day 30, 60, and 90 visits) or early discontinued from study. Primary analysis will be performed in an unblinded fashion for analysis purposes while subjects not completing the observation visits will continue to be followed as being blinded to treatment assignment. Final CSR analyses will be performed after the study is completed, and the database is locked.

7.1.4. Multiplicity Adjustment

A fixed-sequence testing procedure will be implemented to control the family-wise type I error rate at 5% for the primary and key secondary endpoints as presented graphically in Figure 1. The hypothesis of superiority on the primary and key secondary efficacy endpoints of FX-322 versus placebo will be tested in the hierarchical order. The primary efficacy endpoint, incidence of subjects who have a Word Recognition in Quiet (Maryland CNC) improvement at Day 90, will be tested first, using the primary analysis approach described in Section 7.3.1. If superiority of FX-322 over placebo in improving speech perception for Word recognition in Quiet (WR) is established, the treatment effect in the key secondary endpoint, WIN improvement based on mean change from baseline in percentage of recognized words overall at Day 90, will be tested subsequently, using the analysis approach described in Section 7.4.2. If superiority of FX-322 over placebo is established for the key secondary endpoint, the treatment effect the next key secondary efficacy endpoint, Patient Global Impression of Change (PGI-C) Hearing Loss Scale responses at Day 90, will be tested subsequently, using the analysis approach described in Section 7.5.2. Lastly, if superiority of FX-322 over placebo is established for the previous three endpoints, the treatment effect for PGI-C Daily Impacts Scale responses at Day 90 will be tested subsequently, using the analysis approach described in Section 7.5.4.

7.1.5. Model Fitting

Inferential statistical methods examining continuous endpoints will be examined via a Mixed-effects Model for Repeated Measures (MMRM). Inferential analyses for categorical endpoints will be analyzed using univariate methods and/or Generalized Estimating Equations (GEE). The MMRM and GEE analyses will employ an unstructured working correlation matrix.

Further details for each of the planned models and analyses are provided in subsequent sections.

7.1.6. Imputation Rules for Partial/Missing Data

Based on previous studies of FX-322, there is expected to be a very minimal amount of missing data in this study. Missing data for endpoints for word recognition in quiet using Carney-Schlauch confidence intervals will be assumed missing at random and will be imputed using the last observation carried forward (LOCF). Missing data for the key secondary endpoint for WIN improvement will be assumed missing at random and will be taken into account using the model-based MMRM approach. Missing data for PGI-C analyses will not be imputed. Missing data for other endpoints will remain missing in the planned statistical summaries and analyses.

7.1.7. Summary of Endpoints and Analysis Methods

To assess treatment effect if no rescue medication is available, for efficacy analyses, assessments performed on or after date of rescue medication or therapy taken during the follow up period will not be included in the analyses. Specifically, rescue medication includes intratympanic steroid administered in the treated ear after study drug administration through Day 90 visit. A summary of endpoints and analysis methods is presented in Table 7-2.

Table 7-2 Endpoints and Analysis Methods

Endpoint	Analysis Method(s)	Section
Word Recognition in Quiet (Maryland CNC) and Word Recognition (W-22)*		7.3

Endpoint	Analysis Method(s)	Section
Improvement from baseline above Carney-Schlauch	 Descriptive summary for treated and untreated ears Brimary Analysis: Chi Square test for treated ears 	7.3.1
upper confidence limits (Primary Endpoint)	 Primary Analysis: Chi-Square test for treated ears Sensitivity Analysis: Chi-Square test for treated ears in PPAS 	
	 Sensitivity Analysis: Chi-Square test for treated ears based on improvement from baseline above 80%, 85%, and 90% Carney-Schlauch upper confidence limits 	
	Sensitivity Analysis: CMH test for treated ears	
	Sensitivity Analysis: GEE in treated ears	
	• Sensitivity Analysis: DerSimonian and Laird (1986) estimation for treated ears using both randomization factors (4 strata) as defined in Section 2.3. If the analysis cannot be computed using both randomization factors, the analysis will be performed using the single randomization factor (2 strata) that produces more similarly sized strata.	
	Scatterplots for treated and untreated ears	
	Descriptive summary for treated ears by site	
Percentage of recognized words	Descriptive summary for treated and untreated ears	7.3.2
Change from baseline in percentage of recognized words	 Descriptive summary for treated and untreated ears Line graphs (with standard error bars) for observed mean change from baseline for treated ears 	7.3.3
Improvement ≥10% (5 words) from baseline in percentage of recognized words	Descriptive summary for treated earsGEE in treated ears	7.3.4
 Line graphs (with standard error bars) for adjusted least squared means in change from baseline for treated ears MMRM in treated ears 		7.3.5
Improvement from baseline above Thornton-Raffin upper confidence limits	 Descriptive summary for treated and untreated ears Scatterplots for treated and untreated ears 	7.3.6
Words-In-Noise*		7.4
Percentage of recognized words	Descriptive summary for treated and untreated ears	7.4.1
Change from baseline in percentage of recognized	Descriptive summary for treated and untreated ears	7.4.2

Version Date: 2023-01-19

Page 20 of 64

Endpoint	Analysis Method(s)	Section
words (Key Secondary Efficacy Endpoint)	• Line graphs (with standard error bars) for adjusted least squared means in change from baseline for treated ears	
	Primary Analysis: MMRM in treated ears	
	• Sensitivity Analysis: MMRM in treated ears for PPAS	
Improvement ≥10% (7 words) from baseline in percentage of recognized words	Descriptive summary for treated earsGEE in treated ears	
Spearman-Kärber estimates of decibel (dB) thresholds for word recognition (25 th , 50 th (median) and 75 th percentiles)	 Descriptive summary for treated ears Scatter plots for treated ears 	7.4.4
Change from baseline in median Spearman-Kärber estimates	 Descriptive summary for treated ears Line graphs (with standard error bars) for adjusted least squared means in change from baseline for treated ears MMRM in treated ears 	
Improvement ≥3 dB shifts in median Spearman-Kärber estimates from baseline	Descriptive summary for treated earsGEE in treated ears	7.4.6
Patient Global Impression of	Severity and Patient Global Impression of Change*	7.5
PGI-S hearing loss scale responses	Descriptive summary for treated ears	7.5.1
PGI-C hearing loss scale responses (Key Secondary Efficacy Endpoint)	Analysis of Covariance (ANCOVA) in treated ears	7.5.2
PGI-S daily impacts scale responses	Descriptive summary for treated ears	7.5.3
PGI-C daily impacts scale responses (Key Secondary Efficacy Endpoint)	ANCOVA in treated ears	7.5.4
Pure Tone Audiometry		7.6
Air Conduction (AC) and Bone Conduction (BC) audiometry dB hearing level (HL) thresholds by frequency	Descriptive summary for treated and untreated ears	7.6.1

Endpoint	Analysis Method(s)	Section
Mean overall pure tone average (PTA) (AC over 0.5, 1, 2, and 4 kHz) and Bone Conduction Average (BCA) (BC over 0.5, 1, 2 and 4 kHz)	Descriptive summary for treated ears	7.6.2
AC and BC improvement ≥10 and ≥15 dB HL from baseline, separately, for two contiguous frequencies	Descriptive summary for treated ears	7.6.3
AC and BC improvement ≥15 and ≥20 dB HL from baseline, separately, for any frequency	Descriptive summary for treated ears	7.6.4
AC and BC composite improvement from baseline	Descriptive summary for treated earsGEE in treated ears	7.6.5
Change from baseline in mean overall PTA and BCA	Descriptive summary for treated ears	7.6.6
Shift from baseline in mean overall PTA categories	Descriptive summary for treated ears	7.6.7
Mean low AC dB HL threshold (AC only over 0.25, 0.5, 1, and 2 kHz frequencies)	Descriptive summary for treated ears	7.6.8
Mean high AC dB HL threshold (AC only over 3, 4, 6, and 8 kHz frequencies)	Descriptive summary for treated ears	7.6.9
Air-Bone Imbalance at 0.5, 1, 2, 3, and 4 kHz	Descriptive summaries for treated ears	7.6.10
Shift from baseline in Air- Bone Imbalance at 0.5, 1, 2, 3, and 4 kHz	Descriptive summary for treated ears	7.6.11
Extended High Frequency Aud	ometry (EHFA)	7.7
AC audiometry dB HL thresholds by frequency	Descriptive summary for treated and untreated ears	7.7.1
Mean dB HL threshold (AC over 9-16 kHz)	Descriptive summary for treated ears	7.7.2
AC improvement ≥10 and ≥15 dB HL from baseline,	Descriptive summary for treated ears	7.7.3

Endpoint	Analysis Method(s)	Section
separately, for two contiguous frequencies		
AC improvement ≥15 and ≥20 dB HL from baseline, separately, for any frequency	Descriptive summary for treated ears	7.7.4
AC composite improvement from baseline	Descriptive summary for treated earsGEE in treated ears	7.7.5
Shift from baseline of no signal to any signal by frequency	Descriptive summary for treated ears	7.7.6
Shift from baseline of no signal to any signal in two contiguous frequencies	Descriptive summary for treated ears	7.7.7
Shift from baseline of no signal to any signal in three contiguous frequencies	Descriptive summary for treated ears	7.7.8
Examination of Subgroups*		7.8
Incidence of WR Improvement from baseline above Carney-Schlauch upper confidence limits	Forest plot	

*Efficacy endpoint

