### **10.9.1 Prohibited Medication/Therapy**

Oral and intratympanic steroids are prohibited through the follow up period [through Visit 6 (Day 90)]. The subject's best medical care should guide the investigator in the management of conditions that develop during the observational period after 90 days. Aminoglycosides and platinum-based chemotherapies are excluded during the study.

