### **10.9.2 Rescue Medication**

No rescue medication will be provided as no FDA approved treatment for sensorineural hearing loss exists. The Investigator should treat any adverse events as medically appropriate and per their standard of care.

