7.2. Primary and Key Secondary Efficacy Endpoint Estimands

7.2.1. Primary Efficacy Endpoint

Variable: Response, defined as improvement from baseline at Day 90 above Carney-Schlauch 95% upper confidence limits in Word Recognition in Quiet (Maryland CNC) in treated ears.

Population: The analysis population will be the FAS.

Intercurrent events: Subjects who discontinue the study early will be considered missing at random, and their last non-missing observation will be carried forward (i.e., if their Day 60 improvement is above Carney-Schlauch 95% upper confidence limit, then their Day 90 results will be assumed to also be above the limit).

Population-level summary: Comparison of responder proportions between treatment groups at the Day 90 visit.

Additional details on the computation, analysis, and sensitivity analyses for the primary endpoint can be found in Section 7.3.1.

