7.3. Word Recognition in Quiet: Maryland CNC and W-22

Word recognition will be measured separately with recorded Maryland CNC and W-22 word lists. Both tests will consist of 50 words presented to the subject and the percentage of words correctly identified will be recorded separately for each test. If all 50 words are not assessed in an ear, the WR test score will not be calculated for that ear.

Word recognition will be performed at the Screening/Start of Lead-In, Lead-In, End of Lead-In/Treatment, Day 30, Day 60, Day 90, Day 180, and Day 270 visits. For Screening/Start of Lead-In, testing will be performed at 30 dB sensation level (SL) regarding the pure tone average of 0.5, 1, and 2 kHz at Screening/Start of Lead-In. For Lead-In and all subsequent visits (End of Lead-In/Treatment, Day 30, Day 60, Day 90, Day 180, and Day 270) testing will be performed at 30 dB SL regarding the pure tone average of 0.5, 1, and 2 kHz at Lead-In. If 30 dB SL is at an uncomfortable listening level for the participant, testing will be performed at the participant's most comfortable listening level. Word lists will be rotated at each visit.

For speech perception, WR in Quiet (Maryland CNC) will be used for the primary analyses. All analyses will be repeated using WR in Quiet (W-22) for supplementary analyses.

Word Recognition in Quiet results will be presented in a data listing for subjects in the FAS.

- 7.3.1. Improvement from baseline above Carney-Schlauch upper confidence limits
 - Computation of the Endpoint

Improvement is defined as an increase in post-baseline WR score above the Carney-Schlauch (2007) 95% upper limit based on baseline (average of Lead-In and End of Lead-In/Treatment scores) assessment. Subjects with improvement will be computed as 1, and as 0, otherwise for each visit and by ear (left, right). Missing values will be imputed using LOCF. Left and right ears will be mapped to treated and untreated for analysis. The incidence of WR improvement will be computed as the proportion of subjects who have a WR in Quiet improvement.

The Carney-Schlauch 95% confidence intervals (2007) reported in Section 14.2 will be used directly and not computed.

• Analysis of the Endpoint

The incidence of WR improvement will be summarized descriptively for treated and untreated ears separately by visit and treatment group for subjects in the FAS.

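### Results after a rescue steroid are dropped and LOCF then fills the primary flag, so a success scored before rescue can count as a Day 90 response

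*SAP*

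**What the plan says.** SAP 7.1.7 gives its purpose as "To assess treatment effect if no rescue medication is available" and then states that "assessments performed on or after date of rescue medication or therapy taken during the follow up period will not be included in the analyses". It goes on to specify that "rescue medication includes intratympanic steroid administered in the treated ear after study drug administration through Day 90 visit". The exclusion has no end date, so read literally it also covers Days 180 and 270.

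For the primary endpoint, the Day 90 Carney-Schlauch responder flag on Maryland CNC in treated ears, SAP 7.3.1 says: "Missing values will be imputed using LOCF". SAP 7.1.6 says the same in general terms. Neither limits LOCF by the reason a value is missing.

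The primary estimand in SAP 7.2.1 names one intercurrent event: "Subjects who discontinue the study early will be considered missing at random, and their last non-missing observation will be carried forward". Its example has a subject above the limit at Day 60 taken as above it at Day 90. Rescue and prohibited steroids are not mentioned.

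Protocol 10.9.1 says: "Oral and intratympanic steroids are prohibited through the follow up period", up to Visit 6 (Day 90). Protocol 10.9.2 says: "No rescue medication will be provided as no FDA approved treatment for sensorineural hearing loss exists".

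**The concern.** The exclusion rule aims at a hypothetical estimand, the outcome had there been no rescue. That is a legitimate target, but LOCF on a binary flag does not estimate it. If hearing in an ear falls after a good score and the ear is then injected, the outcome without rescue is more likely to resemble the fall than the earlier good score. The plan carries the good score.

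Protocol 8.2 lists hearing loss among the risks of intratympanic injection. Protocol section 14 makes a word recognition score below the lower 95% limit of the Visit 3 score an adverse event of special interest (AESI). One ear could therefore be an AESI case and a primary responder in the same report. At stake are the responder rate in the primary test and the completeness of the by-visit word recognition and WIN tables.

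**Working it through.** **1. Inputs and the plan's own figure.** SAP 2.5 gives 112 evaluable subjects and 10% dropout. 112 / (1 - 0.10) = 124.4, which agrees with the stated 124, or 62 per arm. If all are dosed, one flag moves an arm's rate by 1/62 = 1.6 percentage points. The responder rates behind the 80% power are in the restricted addendum, so the power cannot be recomputed.

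**2. The rules applied in order to one ear**

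| Course | Flag at Day 60 | Day 90 score used? | Day 90 flag in primary test |
|---|---|---|---|
| Success at Day 60, decline, intratympanic steroid Day 70 | 1 | No, excluded by 7.1.7 | 1, by LOCF |
| Decline already scored at Day 60, intratympanic steroid Day 70 | 0 | No, excluded by 7.1.7 | 0, by LOCF |
| Success at Day 60, decline, oral steroid Day 70 | 1 | Yes, no rule removes it | As observed |
| Intratympanic steroid before any post-baseline score | none | No | Not defined |

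A score taken on the day of rescue is also excluded, because the rule runs from that date.

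**3. Can an unscheduled test before rescue correct the first row?** Sometimes. SAP section 3 lets an unscheduled assessment stand in when scheduled Day 90 data are absent. SAP 7.1.2 maps unscheduled data by window (Days 2-45, 46-75, 76-135) and uses them only if that visit has no scheduled data. Under 7.1.2, a drop measured on Day 70 belongs to the Day 60 window and is passed over if the Day 60 visit was attended.

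**4. Does a planned analysis test the rule?**
- The 80/85/90% limits, CMH, GEE and DerSimonian-Laird analyses (SAP 7.3.1) use the same endpoint, to which LOCF applies.
- The PPAS repeat would help only if steroid use is classed as a major deviation. SAP sections 4 and 6 do not say so.
- SAP 7.3.4 to 7.3.6 do not impute, but they concern other endpoints. They leave out post-rescue scores and do not count a rescued ear as a failure.

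**5. Expected size.** Expected carried successes per arm = rescued ears x P(last usable flag = 1). Neither term is in the documents. Assume 2-5% rescued and a probability of 10-30%:
- rescued ears: 0.02 x 62 = 1.24 to 0.05 x 62 = 3.1
- carried successes: 1.24 x 0.10 = 0.12 to 3.1 x 0.30 = 0.93
- in points: 0.12/62 = 0.2 to 0.93/62 = 1.5

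The probability could be much lower. A binomial simulation used 50 words, the rounded-up mean of two baselines and the chart in SAP 14.2. An ear with no true change (true score 10% to 80%) was flagged at a given visit 0.8% to 1.3% of the time. At 1.3%, 3.1 rescued ears give 3.1 x 0.013 = 0.04 carried successes.

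**6. What one flag can do.** The test is the uncorrected Pearson chi-square with 62 per arm: z = [(a - b)/62] / sqrt[2p(1 - p)/62], with p = (a + b)/124. For 7 v 1, p = 8/124 = 0.0645, z = 0.0968/0.0441 = 2.19 and the P value is 0.028.

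| Responders, FX-322 v placebo | P value | One FX-322 responder fewer | P value |
|---|---|---|---|
| 7 v 1 | 0.028 | 6 v 1 | 0.052 |
| 15 v 6 | 0.031 | 14 v 6 | 0.051 |

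These counts are chosen at the edge of significance. They show what a single flag can do, not what is expected.

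**The case against.** **The handling is deliberate and blinded.** SAP 7.1.7 declares a no-rescue target, and the rule applies alike to both arms. This stands. The remaining question is whether LOCF serves that target, and the SAP gives no argument that it does. No sentence says that rescue-excluded values are filled by LOCF; that follows from the unqualified wording of 7.1.6 and 7.3.1. Nor do the documents show a bias between arms. Protocol section 7 reports that improvements in FX-322 patients generally appeared within 15-30 days. If that recurred, more early flags would be there to carry on FX-322, but this is conditional.

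**Rescue should be rare.** Steroids are prohibited through Day 90, and SAP 7.1.6 expects very little missing data. This stands and keeps the expected effect small.

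**A reader might infer that harm is hidden.** The documents do not support that. Word recognition, WIN and audiometry results are all listed for the FAS, AESIs are tabulated and listed (SAP 8.4), and removal starts at the rescue date, not at the decline. What is lost is narrower: post-rescue scores leave the word recognition and WIN summary tables. For audiometry the position is unclear, because Table 7-2 does not mark it as efficacy while Protocol 13.1 groups it there.

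**A reader might also infer that oral steroids are handled in contradiction to the protocol.** The SAP does not name oral steroids, so by default data after them are kept. That is an omission. A prohibition and a rescue definition can differ legitimately, and the word includes may be meant as open-ended. The passages still need to be reconciled.

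**Conclusion.** The point holds in a limited form. Taken together, the exclusion and LOCF rules can score an ear as a Day 90 responder on a success recorded before rescue, whatever happened to its hearing afterwards. The effect depends on the last usable flag: a 0 is carried forward just as a 1 is. It rests on reading the LOCF rule as unqualified, which is its natural reading. That a steroid would be given because hearing worsened is an inference; no document states the reason.

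The expected size under the assumed ranges is about 0.1-0.9 subjects per arm, or 0.2-1.5 points. A figure of about 5 points (3.1/62) would need every rescued ear to have been a responder beforehand, and nothing in the documents supports that. The effect is small on average. It still deserves correction, because one flag can decide a close primary result and no planned sensitivity analysis clearly tests the rule.

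**What to change.** This concerns data handling only; no rule on the clinical use of steroids is proposed.

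- **SAP 7.2.1:** list rescue as an intercurrent event and state its handling.
- **SAP 7.1.7 and 7.3.1:** state that LOCF does not carry a value across a rescue date, and say what applies when no post-baseline score precedes rescue.
- **SAP 7.3.1:** add two primary sensitivity analyses, one scoring a subject rescued before Day 90 as a non-responder and one using the observed Day 90 score.
- **SAP 7.3 and 7.4:** produce by-visit descriptive word recognition and WIN tables from all observed data, with rescued ears flagged. State whether the exclusion applies to audiometry.
- **SAP 7.1.7 with Protocol 10.9.1 and 10.9.2:** reconcile these passages and state how data after oral steroid use are handled.

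The cost is some SAP wording, one flag and a few extra runs. The responder rate may come out slightly less favourable.
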